## 4.6 Criteria for Withdrawal

### 4.6.1 Withdrawal of Patients from Treatment

Any patient can withdraw from the treatment at any time without personal disadvantages and without having to give a reason. Patients who discontinue participation in the clinical study on their own or patients who are withdrawn by the investigator, for reasons other than disease progression (i.e. in case of AEs, protocol violations), will be defined as premature withdrawals. Withdrawn patients will be asked to attend a final follow-up visit and to return unused trial medication. Premature withdrawals will not be replaced. The time of treatment discontinuation must be documented in the patient file and on the CRF.

The investigator can also discontinue the participation of a patient in the study after considering the risk-to-benefit ratio, if he/she no longer considers the further treatment of the patient according to study protocol justifiable. The date of and the primary reason for the withdrawal, as well as the observations available at the time of withdrawal, are to be documented on the CRF. Reasons leading to the withdrawal of a patient can include the following (**one primary reason must be determined**):

- **Lack of efficacy** of the experimental intervention
- **Intolerable adverse events** from **both** components of the intervention (intensive blood pressure control **and** ASA-medication), e.g.
  - Any bleeding that results in hospital inpatient treatment
  - Severe skin reaction and/or asthma requiring treatment with medication exceeding a single dose
  - Gastric ulcer, if not possible to manage by gastroprotective co-medication
  - Severe orthostatic hypotension
- Disease progression
  - In patients with 1 intracranial aneurysm, end of treatment applies if aneurysm rupture (SAH) occurs or interventional treatment of the aneurysm (endovascular or neurosurgical). Patients who have multiple aneurysms can stay in the trial if growth, rupture or preventive treatment of 1 aneurysm occurs
- **Lack of patient's cooperation**, e.g.
  - Patient's request to withdraw
  - Lack of compliance, patient fails to attend the interim visits as agreed or perform self-medication according to schedule
- **Other reasons** (noting reason), e.g.
  - Other diagnosis than study disease
  - Did not meet major in-/exclusion criteria (coming to light after randomisation)

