- Existing or intended pregnancy, lactation in patients of the intervention group. If patients in the control group become subsequently pregnant and/or need to breastfeed after randomisation, they will not be excluded from the trial.

All patients who finish the study prematurely will be asked to attend a follow-up visit and to return unused trial medication. The patient must be asked to consent to this last examination. The withdrawal examination will be documented in the CRF.

If a patient does not come to a visit, the patient will be contacted and asked for information. If the patient wants to withdraw and agrees to give explaining reasons, the reason should be documented in the patients file and in the CRF.

In case of early withdrawal, the last aneurysm imaging will be used for the primary outcome analysis (*last observation carried forward*).

If a patient has severe side effects from one component of the intervention only, (e.g. severe orthostatic hypotension from intensive blood pressure control or major gastrointestinal bleeding from ASA), it can be decided to adjust or stop the component of the intervention causing the side effects, while continuing the other component of the intervention.

For documentation of AEs and SAEs see 8.1.6 and 8.2.

| Term                         | Definition   | Comment/ Sample  |
|------------------------------|--|--|
| Drop-out, study              | 
Participation terminated completely, including follow-up
 
Possible reasons:
 
 
• Patient withdraws consent: Withdrawal
 
• Patient moved/cannot be contacted
 
• Interventions cannot be performed due to medical reasons
 
• Non-compliance of patient
 
 
Drop-out after completion of study intervention:
Lost to follow-up
 
Final examination will be performed, if patient agrees. Study-Completion/ Withdrawal-form will be completed.
 | 
ITT-sample
 
ITT-sample (if study intervention completed)
  |
| Drop-out, study intervention | Termination of study intervention, follow-up once as per protocol.   | ITT  |
| Screening-failure            | 
Exclusion criteria given prior to screening / enrolment:
 
Patient will be recorded at screening list, but will not be provided with a patient number.
   | -  |

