## 8.2 Period of Observation and Documentation

Adverse events (AEs) will be ascertained by the investigators using non-leading questions, noted as spontaneously reported by the patients to the medical staff or observed during any measurements on all study days. The observation period begins with the randomisation and ends with the last study visit, 30 days +/-10 days after end of treatment visit (or after withdrawal) (i.e. follow-up-visit). AEs will be documented in the patient file and in the CRF. All subjects who present AEs, whether considered associated with the use of the trial medication or not, will be monitored by the responsible investigator to determine their outcome; this applies to withdrawals too (see also 8.1.7).

The end date of the SAE is defined typically the same as for AEs. The end date of the SAE must not be later than the end date of the corresponding AE.

AEs and SAEs that are on-going at the time of death are considered not resolved or resolving.

The patients should report any AEs occurring during the outpatient part to the study centre by phone.

|   |   |                               |
|---|---|-------------------------------|
| Clinical Trial Code: Protect-U
EudraCT: 2017-000514-35 | Trial Protocol
Version 07 - August 23 - 2022 | Page 44 of 62
CONFIDENTIAL |
|---|---|-------------------------------|

All SAEs and their relevance for the benefit/risk assessment of the study will be evaluated continuously during the study and for the final report. All SAEs will be documented in the "Serious Adverse Event" form (see 8.3).

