#### *Budget Impact Analysis (BIA)*

The design of the budget impact analysis (BIA) will be a study of different scenarios of either or not introducing preventive medication for patients with an aneurysm. The BIA will be based on data collected alongside the clinical study. It will allow estimation of the financial consequences of introduction of both ASA treatment and intensive hypertension control from the perspective of different stakeholders involved. All cost items needed for the BIA will be derived directly from our economic data collection, the valuation of those items depends on the perspective taken for the budget impact analysis. The perspectives to be included in the BIA are (1) net-BKZ or government perspective and (2) the health insurance perspective. Substitution effects, i.e. reduced need for expensive health care after aneurysm rupture will be taken into account. Different scenarios with different levels of implementation of preventive treatments will be analysed and compared, ranging from all patients with a known aneurysm, to patients with larger aneurysms only. The time horizon for the BIA will be 3 years. BIA results will be reported separately for each year within the time horizon and indexation will be applied.

Biometric analysis will be defined in the statistical analysis plan, which has to be authorised before opening the database by the biometrician, the sponsor, and the LKP.

The adjudication committee (PIs and another experts) will review protocol deviations and reach consensus on whether these should be regarded as major or minor, using blinded data if possible.

In addition, this committee will review unclear endpoints, such as sudden deaths and subarachnoid haemorrhage of unknown origin.

Subjects to be included in the analyses are all subjects randomised and thus a full intention to treat analysis.

The additional data provided by patients of the intervention group using blood pressure devices may be displayed in tables for descriptive statistics. They may be examined for their relationship with blood pressure values obtained during trial visits, for description of device utilisation, and for their relationships with outcomes as described above.

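### Section 4.6.1 ends follow-up about 30 days after a patient stops the intervention, which conflicts with the promised intention-to-treat analysis at 36 months and probably costs the intervention arm more outcomes

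*Protocol*

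**What the plan says.** The table of terms in Protocol 4.6.1 has two drop-out statuses.

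- Drop-out from the study: "Participation terminated completely, including follow-up". The possible reasons include withdrawn consent and moving away, but also "Interventions cannot be performed due to medical reasons" and "Non-compliance of patient".
- Drop-out from the study intervention: "Termination of study intervention, follow-up once as per protocol". This group is labelled ITT.

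The list of withdrawal reasons in the same section includes intolerable adverse events from both components, "Lack of compliance, patient fails to attend the interim visits as agreed or perform self-medication according to schedule" and "Existing or intended pregnancy, lactation in patients of the intervention group". Control patients who become pregnant stay in the trial. After early withdrawal, the last aneurysm scan is used for the primary outcome.

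The Clinical Trial Schedule puts the follow-up visit 30±10 days after the end of treatment or withdrawal. Section 8.2 says that adverse event observation "ends with the last study visit, 30 days +/-10 days after end of treatment visit (or after withdrawal").

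On the analysis side, 7.2 defines the primary endpoint within 36±6 months of randomisation. Section 9.2 takes all randomised patients as the primary analysis set, apart from narrow eligibility exceptions. Section 9.3 bases the primary analysis on intention to treat and closes with: "Subjects to be included in the analyses are all subjects randomised and thus a full intention to treat analysis". Section 6.3 foresees a CTA or MRA for all patients at 36±6 months.

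**The concern.** An intention-to-treat analysis needs each patient's outcome whether or not the patient kept to the treatment. Labelling a stopper as ITT keeps that patient in the denominator but does not collect the 36-month outcome.

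The loss is unlikely to be even. Controls receive no trial ASA, no study blood pressure target and no device, so they cannot stop for intolerance of both components or for failed self-medication. The pregnancy rule is one-sided by its own terms. Withdrawn consent, moving away and missed visits can occur in either arm.

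The direction of the error is predictable. Growth found by a given date can only increase with longer imaging. If imaging is cut short more often in the intervention arm and the last scan is carried forward, that arm's observed risk falls for a reason unrelated to benefit. New adverse events that start more than about 30 days after withdrawal are also not collected. The secondary analyses over all available follow-up lose the same person-time.

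**Working it through.** **Does follow-up really end?** The word once might be a slip. Other places point the same way. Section 4.6.1 speaks of a final follow-up visit and of a last examination. The Schedule dates that visit at 30±10 days after withdrawal. Section 8.2 ends adverse event observation there. No sentence requires a later scan or contact for someone who has stopped.

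**The plan's own figure.** Inputs from 9.1: 15% versus 8.25%, alpha 0.05, power 80%. The two-sided test of two proportions with pooled variance and no continuity correction gives 353 per group, as stated. The total of 776 corresponds to 706 × 1.1 = 776.6, that is 388 per arm (4.1). The 10% dropout allowance covers lost numbers, not imbalance: 10% of 776 is about 78 patients, which is 20% of one arm if they all fall there.

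**Illustration with no true effect.**

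- True 36-month risk is 15% in both arms, with 388 per arm.
- d is the share of an arm lost, and f is the share of the 36-month risk already seen on the last scan. Both are assumptions; the protocol gives no rate by arm.
- Observed risk in an arm: p = 0.15 × (1 − d) + 0.15 × d × f.
- SE = √[pI(1 − pI)/388 + pC(1 − pC)/388], and δ = pC − pI.
- Two-sided error = Φ(−1.96 + δ/SE) + Φ(−1.96 − δ/SE).

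Worked case, with 10% loss in the intervention arm only and f = 1/3: pI = 0.135 + 0.005 = 0.140 and pC = 0.150. The risk ratio is 0.140/0.150 = 0.93. SE = 0.0253 and δ/SE = 0.396, so the error is 0.0589 + 0.0092 = 6.8%.

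| Loss, intervention / control | f | pI | pC | Risk ratio | Two-sided error |
|---|---|---|---|---|---|
| 10% / 0% | 1/3 | 0.1400 | 0.1500 | 0.93 | 6.8% |
| 20% / 0% | 1/3 | 0.1300 | 0.1500 | 0.87 | 12.6% |
| 10% / 0% | 1/2 | 0.1425 | 0.1500 | 0.95 | 6.0% |
| 20% / 0% | 1/2 | 0.1350 | 0.1500 | 0.90 | 9.2% |
| 10% / 5% | 1/3 | 0.1400 | 0.1450 | 0.97 | 5.5% |
| 10% / 5% | 1/2 | 0.1425 | 0.14625 | 0.97 | 5.3% |

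This is a two-proportion approximation to the planned Poisson model, and it ignores the interim looks.

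**The case against.** Several points on the other side stand.

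- A reader might infer that the protocol treats stopping the intervention and leaving the trial as the same thing. It does not: the table has two statuses. The fault lies in the single follow-up and in two entries among the reasons for complete drop-out. The withdrawal reasons in 4.6.1 are also permissive, not automatic.
- A reader might infer that the loss is almost confined to the intervention arm. The text supports only a likely excess. Patient request, missed visits, wrong diagnosis, failed eligibility, withdrawn consent and moving away apply to both arms, and in an open-label trial controls may leave too.
- The one-sided route is narrow. A patient who does not tolerate one component can continue the other (4.6.1). Interrupting ASA for surgery, or stopping the IMP while other ASA is prescribed, is not described as leaving (5.4.5). Missing weekly home readings is not a protocol deviation (6.2).
- A reader might infer that patients with no follow-up scan count as event-free (f = 0), which would give risk ratios of 0.90 and 0.80 and errors of 9.2% and 23.1% at 10% and 20% one-arm loss. The protocol does not say so. Growth is defined on serial imaging (7.2), patients imaged with different modalities are treated as dropouts (6.3), and 9.1 separates 776 assigned from 706 analysed. The all-randomised statement in 9.3 leaves the question open, so f = 0 is at most a worst case.
- A reader might infer that harms are lost altogether after stopping. Ongoing adverse events are followed to an outcome in withdrawn patients too (6.4, 8.1.6, 8.2). Only events with a later onset are missed.

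Other text softens the rule without curing it. Section 6.3 foresees a 36-month scan for all patients and upload of later imaging, and 6.4 has missing images retrieved at the follow-up visit. None of this obliges a site to collect anything after withdrawal, and the carry-forward rule presumes that the scan may be absent. The follow-up examinations allowed in the protocol-deviation row of the 4.6.1 table are optional and concern eligibility or diagnosis. A statistical analysis plan may refine the handling of missing outcomes, but it cannot recover outcomes that were never collected.

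**Conclusion.** The point holds as a conflict within the protocol. Section 4.6.1, the Schedule and 8.2 close observation about a month after withdrawal, while 7.2, 9.2 and 9.3 need a 36±6-month outcome from everyone randomised and 6.3 expects the scan. With the last scan carried forward, any excess loss in the intervention arm biases the result in its favour.

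The size is uncertain. Under no true effect, the two-sided error runs from about 5.3% (10% versus 5% loss, half the risk observed) to 12.6% (20% loss in the intervention arm only, one third observed), with risk ratios from 0.97 to 0.87. The upper end puts the whole trial-wide dropout allowance in one arm. All cases assume that those lost have the same underlying risk as those who stay. If loss is balanced between arms, this null bias disappears, though outcomes are still lost.

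The planned last subject out is Q2 2029 (3.2), so on the protocol's timetable there was room to amend before outcomes were lost.

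**What to change.** In the 4.6.1 table, replace the single follow-up with continued follow-up to month 36 and study end for anyone who stops the intervention without withdrawing consent: six-monthly contact with telephone allowed, upload of routine CTA/MRA, and adverse event collection. Remove medical inability to have the interventions and non-compliance from the reasons for ending follow-up. When consent is withdrawn, ask permission to go on using routine imaging and records. Align the Clinical Trial Schedule, the text of 4.6.1 on the final visit, and 8.2. The clinical reasons for stopping treatment are not touched.

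The cost is a protocol amendment, a revised withdrawal form and a few extra contacts for patients who stop. Imaging is standard of care, and 6.3 already accepts telephone visits in defined cases.

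Patients who stop will then dilute the observed effect, as intention to treat intends. The apparent power may fall, but the estimate will describe the strategy as randomised.

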#### 4.6.2 Premature Closure of the Clinical Trial or a Centre

If new information on the risk-to-benefit ratio of the drug or on the treatment methods used in the study is obtained in the meantime and safety concerns arise, the sponsor reserves the right to interrupt or terminate the project according to the recommendation of the DSMB and after consultation of the steering committee. Premature termination is also possible if the sponsor or steering committee notices and agrees upon that patient recruitment is insufficient and that this cannot be expedited by appropriate measures.

The DSMB can recommend interruption or termination of the study or of treatment arms based on the results of the intermittent SAE evaluation or of accumulating information on the above mentioned reasons.

Premature termination of a single centre is also possible if the sponsor notices that the conduction of the trial is not compliant with ICH-GCP and / or is not according to the protocol, the patient recruitment and / or the quality of the data is insufficient.

The ethics committee (EC) and the competent authorities must be informed about the premature closure of the trial or one of the treatment arms. Furthermore, the ethics committee(s) and competent authorities themselves may decide to stop or suspend the trial.

All involved investigators have to be informed immediately about a cessation / suspension of the trial. The decision is binding to all trial centres and investigators.

When the trial is closed, all study materials (e.g. blood pressure devices) must be sent to the sponsor.

## 5 INVESTIGATIONAL MEDICINAL PRODUCT (IMP)

### 5.1 Study medication

#### 5.1.1 General Information

The sponsor (UMM) will provide the quantity of trial medication required for the clinical trial sites in Germany and the Netherlands.

Supply of IMP in additional countries will be managed by the national coordinators in accordance with the national regulations.

The medication provided must be used only in the context of this clinical trial. Careful records will be kept of the trial medication supplied to the centres and distributed to the patients. If deficiencies of the trial medication are noticed, the monitor and the project manager must be informed immediately.

Blood pressure lowering drugs will not be part of the IMP. The general practitioner will control the blood pressure target and prescribe blood pressure lowering drugs. The general practitioner can decide himself/herself on the type of antihypertensive drug(s) he/she wants to use to decrease the blood pressure.

#### 5.1.2 Characterisation of study medication

The study medication is:

|  |   |
|--|---|
| International Nonproprietary Name (INN): | Acetylsalicylic acid                              |
| ATC code:                                | B01AC06   |
| Pharmaceutical formulation:              | Tablets   |
| Dose                                     | Daily, 81 – 100 mg (depending on country)         |
| Mode of administration:                  | Oral  |
| Storage instructions:                    | Store below 30°C / 86° F, protected from humidity |

### 5.2 Packaging and Labelling

The trial medication will be used in the original packaging, and labelled specifically for the clinical trial. Labelling in accordance to local regulations may be performed by qualified/authorized pharmacies.

### 5.3 Supplies and Drug Accountability

Supply with trial medication and blood pressure measurement devices in Germany and the Netherlands will be performed by the Pharmacy of the University Hospital Heidelberg by ordering using the IMP order form. Shipment of study medication and blood pressure measurement devices in Germany and the Netherlands will be without temperature control to each site. The investigator will confirm correct receipt of the trial medication in writing and ensure that the medication is stored safely and correctly. The trial medication must be carefully stored in accordance with manufacturer's instructions at the study sites and at the patients' home, in a locked area with restricted access, separately from other drugs, and kept out of the reach and sight of children. The investigator will document the distribution and return of the trial medication

to the patient with the date, recording the quantity distributed and used on the forms provided for this purpose. The site monitor will periodically check the supplies of trial medication held by the investigator to ensure the correct accountability of all trial medication used. Documented destruction of used and unused IMP will take place locally at the sites. It will be assured that a final report of the drug accountability is prepared and maintained by the investigator.

National regulations will be observed regarding provision, handling and labelling of trial medication. Blood pressure devices may be obtained locally.

Study medication handed to patients during a visit must not have an expiry date prior to the date of the next scheduled visit for this patient. Stored study medication will be destroyed at the centres as soon as the durability no longer exceeds 6 months.

## 5.4 Administration of study medication

### 5.4.1 Assignment of Identification Codes

All patients who seem suitable for study participation and take part in the screening will receive a screening number. At the end of the screening phase the eligibility of the patient is assessed finally.

When the patient is included in the study (all inclusion criteria fit and none of the exclusion criteria), he/she will be given a patient study number. This will consist of a number coding the trial centre and the randomisation number generated by the online randomising tool. Patients withdrawn from the study retain their patient number. New patients must always be allocated a new randomisation number.

For allocation to a treatment arm (randomisation) see 5.5.

### 5.4.2 Dosage Schedule

The study medication is given only to patients who have consented to study participation and who are randomized to the intervention group.

Maximum duration of treatment: 120 months  
Maximum dose allowed: 100mg ASA daily, orally

### IMP Compliance

IMP accountability (supply and return) will be documented at each visit, according to the trial schedule. Respective numbers will be transferred in the CRF. Additionally, investigators must provide a statement regarding patients' over-all compliance at the end of the treatment.

